**7.1.5. Adverse events of specific interest (Potential immune-mediated diseases)**

Potential immune-mediated diseases (pIMDs) are a subset of AEs that include autoimmune diseases and other inflammatory and/or neurologic disorders of interest which may or may not have an autoimmune aetiology. AEs that need to be recorded and reported as pIMDs include those listed in [Table 23](#).

However, the investigator will exercise his/her medical and scientific judgement in deciding whether other diseases have an autoimmune origin (i.e. pathophysiology involving systemic or organ-specific pathogenic autoantibodies) and should also be recorded as a pIMD.

**CONFIDENTIAL**208851 (RSV OA=ADJ-002)  
Protocol Amendment 1 Final**Table 23 List of potential immune-mediated diseases**

Neuroinflammatory disorders	Musculoskeletal disorders	Skin disorders

 
• Cranial nerve neuropathy, including paralysis and paresis (e.g. Bell's palsy).
 
• Optic neuritis.
 
• Multiple sclerosis.
 
• Transverse myelitis.
 
• Guillain-Barré syndrome, including Miller Fisher syndrome and other variants.
 
• Acute disseminated encephalomyelitis, including site specific variants e.g.: non-infectious encephalitis, encephalomyelitis, myelitis, myeloradiculoneuritis.
 
• Myasthenia gravis, including Lambert-Eaton myasthenic syndrome.
 
• Demyelinating peripheral neuropathies including: 
 
– Chronic inflammatory demyelinating polyneuropathy,
 
– Multifocal motor neuropathy
 
– Polyneuropathies associated with monoclonal gammopathy.
 
 
 
• Narcolepsy.
 
	
 
• Systemic lupus erythematosus and associated conditions
 
• Systemic scleroderma (Systemic sclerosis), including: 
 
– Diffuse Scleroderma
 
– CREST syndrome
 
 
 
• Idiopathic inflammatory myopathies, including: 
 
– Dermatomyositis
 
– Polymyositis
 
 
 
• Anti-synthetase syndrome.
 
• Rheumatoid Arthritis and associated conditions including: 
 
– Juvenile Idiopathic Arthritis
 
– Still's disease.
 
 
 
• Polymyalgia rheumatica.
 
• Spondyloarthropathies, including: 
 
– Ankylosing Spondylitis,
 
– Reactive Arthritis (Reiter's Syndrome),
 
– Undifferentiated Spondyloarthritis,
 
– Psoriatic Arthritis,
 
– Enteropathic arthritis.
 
 
 
• Relapsing Polychondritis.
 
• Mixed Connective Tissue disorder.
 
• Gout.
 
	
 
• Psoriasis.
 
• Vitiligo.
 
• Erythema nodosum.
 
• Autoimmune bullous skin diseases (including pemphigus, pemphigoid and dermatitis herpetiformis).
 
• Lichen planus.
 
• Sweet's syndrome.
 
• Localised Scleroderma (Morphea).
 

## CONFIDENTIAL

208851 (RSV OA=ADJ-002)  
Protocol Amendment 1 Final

Vasculitis	Blood disorders	Others

 
Large vessels vasculitis including: 
 
Giant Cell Arteritis (Temporal Arteritis),
 
Takayasu's Arteritis.
 
 
 
Medium sized and/or small vessels vasculitis including: 
 
Polyarteritis nodosa,
 
Kawasaki's disease,
 
Microscopic Polyangiitis,
 
Wegener's Granulomatosis (granulomatosis with polyangiitis),
 
Churg–Strauss syndrome (allergic granulomatous angiitis or eosinophilic granulomatosis with polyangiitis),
 
Buerger's disease (thromboangiitis obliterans),
 
Necrotizing vasculitis (cutaneous or systemic),
 
anti-neutrophil cytoplasmic antibody (ANCA) positive vasculitis (type unspecified),
 
Henoch-Schonlein purpura (IgA vasculitis),
 
Behcet's syndrome,
 
Leukocytoclastic vasculitis.
 
 
 
	
 
Autoimmune hemolytic anemia.
 
Autoimmune thrombocytopenia.
 
Antiphospholipid syndrome.
 
Pernicious anemia.
 
Autoimmune aplastic anemia.
 
Autoimmune neutropenia.
 
Autoimmune pancytopenia.
 
	
 
Autoimmune glomerulonephritis including: 
 
IgA nephropathy,
 
Glomerulonephritis rapidly progressive,
 
Membranous glomerulonephritis,
 
Membranoproliferative glomerulonephritis,
 
Mesangioproliferative glomerulonephritis.
 
Tubulointerstitial nephritis and uveitis syndrome.
 
 
 
Ocular autoimmune diseases including: 
 
Autoimmune uveitis
 
Autoimmune retinitis.
 
 
 
Autoimmune myocarditis.
 
Sarcoidosis.
 
Stevens-Johnson syndrome.
 
Sjögren's syndrome.
 
Alopecia areata.
 
Idiopathic pulmonary fibrosis.
 
Goodpasture syndrome.
 
Raynaud's phenomenon.
 

Liver disorders	Gastrointestinal disorders	Endocrine disorders

 
Autoimmune hepatitis.
 
Primary biliary cirrhosis.
 
Primary sclerosing cholangitis.
 
Autoimmune cholangitis.
 
	
 
Inflammatory Bowel disease, including: 
 
Crohn's disease,
 
Ulcerative colitis,
 
Microscopic colitis,
 
Ulcerative proctitis.
 
 
 
Celiac disease.
 
Autoimmune pancreatitis.
 
	
 
Autoimmune thyroiditis (Hashimoto thyroiditis).
 
Grave's or Basedow's disease.
 
Diabetes mellitus type I.
 
Addison's disease.
 
Polyglandular autoimmune syndrome.
 
Autoimmune hypophysitis.
 

When there is enough evidence to make any of the above diagnoses, the AE must be reported as a pIMD. Symptoms, signs or conditions which might (or might not) represent the above diagnoses, should be recorded and reported as AEs but not as pIMDs until the final or definitive diagnosis has been determined, and alternative diagnoses have been eliminated or shown to be less likely.

**CONFIDENTIAL**208851 (RSV OA=ADJ-002)  
Protocol Amendment 1 Final

In order to facilitate the documentation of pIMDs in the eCRF, a pIMD standard questionnaire and a list of preferred terms (PTs) and PT codes corresponding to the above diagnoses will be available to investigators at study start.

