Paper diary cards will be used by the subjects to capture the details of the unsolicited signs or symptoms. They will be reviewed by the investigator at the subsequent study visits (Day 8, Day 31, Day 68 or Day 91) and then reported as applicable in the AE section of the eCRF.

The subject should be trained on how and when to complete each field of the electronic and paper diary. If a subject is illiterate or unable or not willing to complete the electronic and/or the paper him/herself, he/she may be helped by a designate (refer to the [glossary of terms](#) for the definition of designate).

Subject Diary training should be directed at the individual(s) who will perform the measurements of AEs and who will enter the information into the Subject Diary. If a designate enters information into the Subject Diary, this person's identity must be documented in the subject's source record. Any individual that makes entries into the Subject Diary must receive training on completion of the Subject Diary at the time of the visit when Subject Diary is dispensed. This training must be documented in the subject's source record.

The same individual should complete the Subject eDiary throughout the course of the study. The subject should be trained on how to self-measure local solicited AEs and body temperature. The measurement of solicited local AEs is to be performed using the ruler provided by the site.

**7.3.1. Time period for detecting and recording adverse events, serious adverse events and pregnancies****For Part A and Part B:**

All AEs starting within 30 days following administration of each dose of study vaccine (the day of vaccination and 29 subsequent days) must be recorded into the appropriate section of the eCRF, irrespective of intensity or whether or not they are considered vaccination-related.

All AEs/SAEs leading to withdrawal from the study will be collected and recorded from the time of the first receipt of study vaccine until the subject is discharged from the study.

The time period for collecting and recording SAEs will begin at the first receipt of study vaccine and will end 1 month following administration of the last dose of study vaccine for each subject in Part A and 12 months following administration of the last dose of study vaccine for each subject in Part B. See Section [7.4](#) for instructions on reporting of SAEs.

**CONFIDENTIAL**208851 (RSV OA=ADJ-002)  
Protocol Amendment 1 Final

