### **7.5. Follow-up of adverse events, serious adverse events, and pregnancies**

#### **7.5.1. Follow-up of adverse events and serious adverse events**

##### **7.5.1.1. Follow-up during the study**

After the initial AE/SAE report, the investigator is required to proactively follow each subject and provide additional relevant information on the subject's condition to GSK Biologicals (within 24 hours for SAEs; refer to [Table 27](#)).

All SAEs and pIMDs (serious or non-serious) documented at a previous visit/contact and designated as not recovered/not resolved or recovering/resolving will be reviewed at subsequent visits/contacts until the last visit of the subject.

All AEs documented at a previous visit/contact and designated as not recovered/not resolved or recovering/resolving will be reviewed at subsequent visits/contacts until 30 days after the last vaccination.

**CONFIDENTIAL**208851 (RSV OA=ADJ-002)  
Protocol Amendment 1 Final**7.5.1.2. Follow-up after the subject is discharged from the study**

The investigator will follow subjects with SAEs, pIMDs (serious or non-serious), or subjects withdrawn from the study as a result of an AE, until the event has resolved, subsided, stabilised, disappeared, or until the event is otherwise explained, or the subject is lost to follow-up.

If the investigator receives additional relevant information on a previously reported SAE, he/she will provide this information to GSK Biologicals using an electronic Expedited Adverse Events Report and/or pregnancy report as applicable.

GSK Biologicals may request that the investigator performs or arranges the conduct of additional clinical examinations/tests and/or evaluations to elucidate as fully as possible the nature and/or causality of the AE or SAE. The investigator is obliged to assist. If a subject dies during participation in the study or during a recognised follow-up period, GSK Biologicals will be provided with any available post-mortem findings, including histopathology.

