#### For Part B only:

- Occurrence of pIMDs from Dose 1 up to 30 days after the second vaccine dose (Day 91).

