### 10.12.1. Sequence of analyses

In preparation of the planned IDMC evaluations, analyses of all available safety data (as clean as possible) will be performed (see Section 7.10 for more information). The blinded analyses will be done by the GSK study statistician and distributed to the study team. The unblinded analyses will be done by an Independent External Statistician (IES) to maintain the study blind and will be shared with IDMC members through a secured folder (refer to the IDMC charter). Only the outcome of the IDMC reviews will be communicated to the RSV study team (no safety signal or safety signal). No clinical study report will be written at this stage.

The analyses will be performed stepwise:

- A first analysis will be performed on all data available and as clean as possible, when data for at least primary and secondary endpoints up to Day 91 are available (except for cell-mediated immune response at pre-Dose 2 [Day 61] in Part A and Part B and the occurrence of RSV RTI in Part B). This will include results from all subjects in Part A and Part B. This analysis will be considered as final for those endpoints. A clinical study report will be written.

At this point, the statistician will be unblinded (i.e., individual subject treatment assignments will be available), but no individual listings will be provided to the study team. Given that summary safety results may unblind some specific subjects, the study will be considered as single-blind from this point onwards, with subjects remaining blinded up to study end (Visit 8, Month 14). The investigators will not be provided with the individual data listings or with the randomization listings until the end of study analysis.

*During the last study visit, blood samples will be collected only from a subset of subjects (N≈460, all subjects in part B1 and subjects who received a selected level of antigen dose and Placebo in part B2). Therefore, the investigators, site and study staff will be partially unblinded at group level, but not at the individual level.*

*In case there will be an extension study planned, with all or a subset of participants included, the investigators may be provided with the list of study subjects eligible to participate in such study, before the parent study ends.*

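### Suspected pIMDs are to be held as AEs, but non-serious AEs need be recorded on only 60 of about 425 days, and the Day 91 pIMD count is closed at the first analysis

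*Protocol*

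**What the plan says.** Section 7.1.5 lists the pIMD diagnoses in Table 23. It says that signs or symptoms which might turn out to be one of them "should be recorded and reported as AEs but not as pIMDs until the final or definitive diagnosis has been determined", and alternatives have been ruled out or made less likely.

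The AE record to which these cases are sent is limited in time. Section 7.3.1 covers "All AEs starting within 30 days following administration of each dose of study vaccine", and Table 25 shows this as Days 1-30 and Days 61-90. Outside those days Table 25 keeps open SAEs, AEs leading to withdrawal, confirmed pIMDs and intercurrent medical conditions, all to Month 14.

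Follow-up differs by label. Under Section 7.5.1.1, unresolved SAEs and pIMDs are reviewed until the subject's last visit, whereas other unresolved AEs "will be reviewed at subsequent visits/contacts until 30 days after the last vaccination". After discharge, Section 7.5.1.2 covers SAEs, pIMDs and subjects withdrawn because of an AE.

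In Part B, occurrence of pIMDs from Dose 1 to Day 91 is a primary endpoint (Section 10.1), and from Dose 1 to the end of follow-up a secondary endpoint (Section 10.2). The first analysis takes primary and secondary data to Day 91, and Section 10.12.1 adds: "This analysis will be considered as final for those endpoints".

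**The concern.** Section 1.3.1 names pIMDs as the theoretical risk of the adjuvanted formulations, and they are the protocol's only adverse events of specific interest. Many Table 23 conditions, such as vitiligo, coeliac disease or thyroiditis, need not be serious when they begin and may take time to confirm. The protocol deals with that interval by parking the case as an AE, then does not require the AE to be recorded or followed for most of the study.

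Two things are at stake. A suspected case can drop out of sight before anyone confirms or excludes it. And the primary Day 91 count can be closed before an event that began inside its window has been confirmed. With about 100 subjects per formulation, one or two cases are a visible part of the safety picture.

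**Working it through.** **The plan's own figure.** The protocol gives no figure for pIMD ascertainment. The nearest is Section 10.4: with 100 subjects per group, an 80% or 90% chance of at least one AE at true rates of 1.6% or 2.3%. Using 1 − (1 − p)^100, this gives 80.1% and 90.2%, so the figures reproduce.

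**Days on which a non-serious AE must be recorded.**
- Recording windows (Section 7.3.1, Table 25): 30 + 30 = 60 days.
- Follow-up in Part B (Table 8, optimal intervals): Visit 1 to Visit 4, 60 days, plus Visit 4 to Visit 8, 365 days = 425 days.
- Share: 60/425 = 14.1%.
- Over the allowed intervals: 55 + 350 = 405 days gives 60/405 = 14.8%; 75 + 395 = 470 days gives 60/470 = 12.8%.

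This share applies only to non-serious AEs that do not lead to withdrawal. SAEs have their own period to Month 14, and for withdrawals Section 7.3.1 says: "All AEs/SAEs leading to withdrawal from the study will be collected and recorded from the time of the first receipt of study vaccine".

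**Three non-serious cases, none leading to withdrawal, taken through the text.**

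| Onset | Confirmed | AE record required? | Follow-up while only suspected | Primary (Day 91) | Secondary |
|---|---|---|---|---|---|
| Day 45 | Month 6 | No | None required | Not stated; first analysis is final | Counted |
| Day 70 | Month 6 | Yes | Stops 30 days after the last dose | Not stated; first analysis is final | Counted |
| Month 12 | Month 15 | No | None required, before or after Visit 8 | Not applicable | No required route |

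An event with onset on Day 91 can take up to 425 − 91 = 334 days to confirm and still enter the secondary endpoint.

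**Sensitivity, on assumptions only.** The documents give no interval from onset to diagnosis. Suppose onset is uniform over a window of W days, the lag is a fixed L days, and counting stops at the end of the window. The share not yet confirmed is then L/W:
- Day 91 window: 14/91 = 15%, 30/91 = 33%, 60/91 = 66%.
- Whole follow-up: 14/425 = 3%, 30/425 = 7%, 60/425 = 14%.

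Under these assumptions the Day 91 shares are upper limits, because the first analysis waits for all subjects' Day 91 data and earlier enrollees have longer to be diagnosed. If 25% of events were missed at a true rate of 1.6%, the chance of at least one in 100 would be 1 − (1 − 0.012)^100 = 70% instead of 80%. None of these is an estimate for this trial.

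**The case against.** A reader might infer that the pIMD endpoints as a whole miss events whose diagnosis lags onset, or that about 86% of follow-up (100% − 14%) cannot capture a pIMD. The documents do not support either reading.

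- Confirmed pIMDs have their own recording period, Day 1 to Month 14 (Table 25), and are recorded at every Part B visit (Table 7). No earlier AE entry is needed. The short AE window limits where a provisional case is logged, not whether a confirmed one is.
- A late diagnosis made by Month 14 enters the secondary endpoint, the whole-study pIMD table (Section 10.8) and the end-of-study report (Section 10.12.1).
- The endpoints are not stated to count at diagnosis. Section 7.4.1 speaks of pIMDs that occur in the period being reported once the investigator determines that they qualify, which points to dating by occurrence.
- Full certainty is not required. It is enough that "alternative diagnoses have been eliminated or shown to be less likely".
- Section 6.7 puts intercurrent medical conditions in the AE section of the eCRF to Month 14, and Section 7.4.6 allows new pIMD information on paper after eCRF write access is removed.

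The first four points stand and narrow the concern. The fifth helps only in part: intercurrent conditions qualify only if they can alter the immune response or status, and Section 7.4.6 permits late reporting without requiring anyone to follow a case that is still only suspected. Nothing in the objection reconciles Section 7.1.5 with Sections 7.3.1 and 7.5.1, or says what becomes of the Day 91 count once it has been called final.

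**Conclusion.** The concern holds in a limited form. Section 7.1.5 relies on an AE record and AE follow-up that Sections 7.3.1 and 7.5.1 do not require for non-serious suspected cases on about 86% of study days, or once the case is still open at Day 91 or Visit 8. Followed as written, the final status of the first analysis can leave a pIMD with onset by Day 91 out of the primary count. Cases still unconfirmed at Visit 8 have no required route to being counted at all.

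The 14% coverage figure follows from the protocol. The size of any undercount does not: it depends on diagnostic delay, which is not given, and on when the first analysis is cut. There is also no basis for saying that the loss differs between groups. The primary Day 91 endpoint is the more exposed of the two; the secondary endpoint loses only cases not confirmed by Month 14.

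**What to change.** 1. State that pIMDs are assigned to the Day 91 and end-of-follow-up windows by date of onset. Repeat the Day 91 pIMD table in the end-of-study analysis, and exempt that endpoint from the statement in Section 10.12.1 that the first analysis is final.
2. Reconcile Section 7.1.5 with Sections 7.3.1 and 7.5.1. AEs under work-up for a Table 23 diagnosis should be recorded whenever they start between Dose 1 and Visit 8, reviewed at later visits, and carried into the existing Section 7.5.1.2 follow-up until confirmed or excluded. No new reporting category is needed.

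Amendment 1 treats Visit 8 as the remaining scheduled visit, so the recording change acts mainly there. Dating by onset, the repeated table and follow-up of cases open at Visit 8 are all still available.

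The cost is protocol wording, one repeated table, a few more AE entries and a few open cases to follow. The Day 91 pIMD count may rise slightly between the first and final reports, and the final report should explain why.

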## **7.2. Events or outcomes not qualifying as adverse events or serious adverse events**

### **7.2.1. Pregnancy in Part A**

In Part A, female subjects who are pregnant or lactating at the time of vaccination must not receive additional doses of study vaccine but may continue other study procedures at the discretion of the investigator.

While pregnancy itself is not considered an AE or SAE, any adverse pregnancy outcome or complication or elective termination of a pregnancy for medical reasons will be recorded and reported as an AE or an SAE.

Note: The pregnancy itself should always be recorded on an electronic pregnancy report.

The following should always be considered as SAE and will be reported as described in Sections [7.4.1](#) and [7.4.3](#):

- Spontaneous pregnancy loss, including:
  - spontaneous abortion, (spontaneous pregnancy loss before/at 22 weeks of gestation)
  - ectopic and molar pregnancy
  - stillbirth (intrauterine death of foetus after 22 weeks of gestation).

Note: the 22 weeks cut-off in gestational age is based on WHO-ICD 10 noted in the EMA Guideline on pregnancy exposure [[EMA](#), 2006]. It is recognized that national regulations might be different.

- Any early neonatal death (i.e., death of a live born infant occurring within the first 7 days of life).
- Any congenital anomaly or birth defect (as per [[CDC MACDP](#)] guidelines) identified in the offspring of a study subject (either during pregnancy, at birth or later) regardless of whether the foetus is delivered dead or alive. This includes anomalies identified by prenatal ultrasound, amniocentesis or examination of the products of conception after elective or spontaneous abortion.

Furthermore, any SAE occurring as a result of a post-study pregnancy AND considered by the investigator to be reasonably related to the study vaccine will be reported to GSK Biologicals as described in Section [7.4.3](#). While the investigator is not obligated to actively seek this information from former study participants, he/she may learn of a pregnancy through spontaneous reporting.

**CONFIDENTIAL**208851 (RSV OA=ADJ-002)  
Protocol Amendment 1 Final**7.3. Detecting and recording adverse events, serious adverse events and pregnancies**

Electronic Diaries (eDiaries) will be used by the subjects to capture solicited AE data and to notify investigators if other (unsolicited) signs or symptoms were experienced.

Paper diary cards will be used by the subjects to capture the details of the unsolicited signs or symptoms. They will be reviewed by the investigator at the subsequent study visits (Day 8, Day 31, Day 68 or Day 91) and then reported as applicable in the AE section of the eCRF.

The subject should be trained on how and when to complete each field of the electronic and paper diary. If a subject is illiterate or unable or not willing to complete the electronic and/or the paper him/herself, he/she may be helped by a designate (refer to the [glossary of terms](#) for the definition of designate).

Subject Diary training should be directed at the individual(s) who will perform the measurements of AEs and who will enter the information into the Subject Diary. If a designate enters information into the Subject Diary, this person's identity must be documented in the subject's source record. Any individual that makes entries into the Subject Diary must receive training on completion of the Subject Diary at the time of the visit when Subject Diary is dispensed. This training must be documented in the subject's source record.

The same individual should complete the Subject eDiary throughout the course of the study. The subject should be trained on how to self-measure local solicited AEs and body temperature. The measurement of solicited local AEs is to be performed using the ruler provided by the site.

**7.3.1. Time period for detecting and recording adverse events, serious adverse events and pregnancies****For Part A and Part B:**

All AEs starting within 30 days following administration of each dose of study vaccine (the day of vaccination and 29 subsequent days) must be recorded into the appropriate section of the eCRF, irrespective of intensity or whether or not they are considered vaccination-related.

All AEs/SAEs leading to withdrawal from the study will be collected and recorded from the time of the first receipt of study vaccine until the subject is discharged from the study.

The time period for collecting and recording SAEs will begin at the first receipt of study vaccine and will end 1 month following administration of the last dose of study vaccine for each subject in Part A and 12 months following administration of the last dose of study vaccine for each subject in Part B. See Section [7.4](#) for instructions on reporting of SAEs.

**CONFIDENTIAL**208851 (RSV OA=ADJ-002)  
Protocol Amendment 1 Final

In addition to the above-mentioned reporting requirements and in order to fulfil international reporting obligations, SAEs that are related to study participation (i.e., protocol-mandated procedures, invasive tests, a change from existing therapy) or are related to a concurrent GSK medication/vaccine will be collected and recorded from the time the subject consents to participate in the study until she/he is discharged from the study.

